9.5 Data Analysis Sets

Full Analysis Set / Safety Analysis Set (SA)

The safety analysis (SA) set includes all subjects who were enrolled and underwent study procedures in with data available for analysis.

9.5.1 Performance Analysis Set (PA)

Because each monitoring modality sometimes fails to generate clinically interpretable data, rules were applied to facilitate statistical analysis.

The performance analysis set will consist of all subjects who finished the study without major protocol violations and had at least 1 minute of data where a signal was recorded and detected with both devices at the same time. Possible reasons for exclusion of a data point from this analysis set may include but are not limited to the following:

Invalid signal in one of the systems, i.e PregSense™ and the CTG system due to:

1. Device malfunction
2. Maternal movement
3. Device positioning does not enable signal recording
4. Interaction between devices

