5.2.1 Criteria for Early Discontinuation

Subjects who prematurely discontinue the study should be followed and treated by the investigator in a customary manner.

A subject may withdraw or be withdrawn from the study for the following reasons:

- Subject withdrew consent.
- Request of Sponsor to terminate the study.
- Request of primary care physician or investigator.
- Subject is non-compliant with study procedures.
- Protocol violation.
- Subject is unable to continue the study.
- Subject experiences an adverse event (whether considered related to the investigational product or not) that results in a medical condition that may prevent the subject from meeting study criteria.
- Death.

Reasons for premature withdrawal from the study must be stated in the CRF and in the site source documentation.

If there is more than one reason for early withdrawal from the study, all the reports should be stated.

The study may be stopped following an unexpected event, which does not permit continuation of the study. The Investigator and/or the Sponsor and/or local EC and/or regulatory authority/Competent Authorities can decide to terminate the study.

The data collected up until the withdrawal point will be valid and available for insertion into the study database and the development of the analysis.

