7.2.1 Recording

The PregSense™ will be connected and operated in the most continuous manner as possible recording the fetal cardiac activities and maternal cardiac activities, unless there is a necessity to disconnect the subject due to medical treatment or nursing reasons.

The data will include the following:

- Fetal HR
- Maternal HR
- Uterine activity

The PregSense™ records will be identified by the subject's trial identification number.

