7.5 End of study/Completion of study

Completion of study will be defined by the subject compliance, thus, subjects who finished the study without protocol violations and had at least 1 minute of data where a signal was recorded and detected with both devices at the same time.

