9.5.2 Statistical Analysis of Analysis Sets

The SA set will serve as the analysis set safety assessments. The performance assessments will be performed on the PA set.

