9.6.6 Handling of missing data

No imputation of missing values will be performed. Each subject is expected to contribute at least one data point to the analysis of the primary endpoint, therefore only missing data points will be excluded from the analysis of the relevant endpoint.

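### Section 9.5.1 limits the only performance set to women who finished the study, while 5.2.1 counts data up to withdrawal as valid for analysis; valid paired minutes from withdrawn women are dropped

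*Combined protocol and SAP*

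**What the plan says.** Section 9.5.1 defines the set at the level of the woman: "The performance analysis set will consist of all subjects who finished the study without major protocol violations". She must also have at least one minute in which both devices detected a signal together. The section then lists reasons for dropping individual data points, such as maternal movement or device malfunction. Section 9.5.2 names no other set for performance: "The performance assessments will be performed on the PA set".

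Section 5.2.1 lists reasons for withdrawal, some of which can arise during a session (for example, "Subject is unable to continue the study"), and closes with: "The data collected up until the withdrawal point will be valid and available for insertion into the study database and the development of the analysis".

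Section 7.5 is the only definition of completion. It refers to "subjects who finished the study without protocol violations and had at least 1 minute of data" with both devices, which is nearly the 9.5.1 wording but without the word major.

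Two further places bear on the point. Section 7.2.1 asks for recording to be as continuous as possible, "unless there is a necessity to disconnect the subject due to medical treatment or nursing reasons". Section 9.6.6 rules out imputation and says "therefore only missing data points will be excluded from the analysis of the relevant endpoint". Section 9.6.3 will tabulate premature terminations and list the subjects excluded from the performance analyses. No analysis on a wider set is planned.

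**The concern.** The quantity of interest is the difference between two devices in the same minute. Each valid paired minute is a complete comparison, and whether the woman later finished has no bearing on it. The plan accepts this elsewhere: 9.4 and 9.5.1 take one paired minute as enough, 9.5.1 removes bad minutes one at a time, and 9.6.4.1 models repeated measurements within a woman. A completion filter on top of these rules adds no control of signal quality. It also conflicts with 5.2.1.

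Two things are at stake. The FHR, MHR and contraction results describe finishers only, and if women who stop early agree less well, the limits of agreement come out too narrow. Second, because completion is not usefully defined, membership of the primary analysis set in an open-label study could be settled by judgement after the data have been seen.

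**Working it through.** **1. The passages side by side**

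| Case | 9.5.1 | 5.2.1 |
|---|---|---|
| Withdrawn at minute 20 with 20 valid paired minutes | Out, with all 20 | 20 minutes valid and available |
| Finisher with 1 valid paired minute | In | Not addressed |
| Disconnected under 7.2.1, not formally withdrawn | Depends on what finished means | Disconnection is not a listed reason |
| Withdrawn before the CTG was applied | Out; no paired minutes | Nothing to add for agreement |

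The first row is a direct conflict. The third is an ambiguity: 7.5 explains completion by the word finished. Section 7.2 sets sessions of at least 30 minutes, whereas 7.5 and 9.4 ask for only one paired minute. The synopsis also allows optional later sessions up to labor, so it is unclear whether a woman who completes the paired session and then withdraws has finished.

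**2. The plan's own sample-size figure**

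Inputs from 9.3 and 9.4: n = 50, mean FHR difference 0.695 bpm, SD 1.15 bpm, limit 7 bpm, two-sided 5%. The check uses the Bland-Altman power method with a non-central t on n − 1 degrees of freedom and one independent difference per woman.

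- SE of a limit = SD × √(1/n + 1.96²/(2(n − 1))). At SD 2.28: 2.28 × √(0.0200 + 0.0392) = 0.555.
- Upper non-centrality = (7 − 0.695 − 1.96 × 2.28)/0.555 = 3.31.
- Power is 90%. At SD 1.15 it exceeds 99.9%.

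Since 2.28/1.15 = 1.98, the claim of 90% power at almost twice the SD reproduces.

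**3. Cost of losing women**

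The documents give no withdrawal rate, so the numbers analysed are assumed. At SD 2.28, power is 90.0% with 50 women, 88.7% with 48, 86.5% with 45 and 82.0% with 40. At SD 1.15 the loss is negligible.

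**4. Cost of selection**

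Assumptions, none from the documents: 10% or 20% of 50 women stop early, each giving 15 paired minutes instead of 30, with the same mean difference and an SD of 5 or 8 bpm. The finisher SD is either the 1.15 bpm of 9.4 or twice that, 2.3 bpm.

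Pooled variance = (n_fin × 30 × SD_fin² + n_stop × 15 × SD_stop²)/(n_fin × 30 + n_stop × 15); upper limit = 0.695 + 1.96 × √variance.

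Worked case (finisher SD 2.3, 20% stopping, SD 8): (40 × 30 × 5.29 + 10 × 15 × 64)/(1200 + 150) = 15,948/1350 = 11.81; SD 3.44; upper limit 7.43 bpm.

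| | Finisher SD 1.15 | Finisher SD 2.3 |
|---|---|---|
| Finishers only | 2.95 | 5.20 |
| 10% stop, SD 5 | 3.84 | 5.63 |
| 10% stop, SD 8 | 4.91 | 6.37 |
| 20% stop, SD 5 | 4.59 | 6.06 |
| 20% stop, SD 8 | 6.34 | 7.43 |

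If women who stop early have the finisher SD, the limit does not move.

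To reach exactly 7 bpm the pooled SD must be (7 − 0.695)/1.96 = 3.217 (variance 10.35). With 20% stopping they supply 150/1350 = 11.1% of the minutes. Their SD would then have to be √((10.35 − 0.889 × 5.29)/0.111) = 7.1 bpm when the finisher SD is 2.3, or √((10.35 − 0.889 × 1.3225)/0.111) = 9.1 bpm when it is 1.15. That is about 3 and 8 times the finisher SD.

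This pools by minutes and ignores variation between women, which the mixed model in 9.6.4.1 would carry. It is a sketch of scale. The documents give no corresponding starting figures for MHR.

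**The case against.** Four counter-arguments deserve weight.

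*Disconnection is not withdrawal.* A reader might infer from 7.2.1 that women taken off the device for medical or nursing care are discarded. The documents do not establish this. Section 5.2.1 does not list disconnection as a reason for withdrawal, and 7.5 and 9.4 require only one paired minute, so a woman disconnected at minute 20 may well count as a finisher. This stands: the loss is clear only for women withdrawn under 5.2.1. For the others the fault is an undefined term.

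*Section 9.6.6 is not a clear contradiction.* Its rule on missing points can be read as applying to women already in the performance set. This also stands. The conflict that holds is with 5.2.1. Even 5.2.1 does not name an analysis set, but with only one set for performance, data said to be available for analysis have nowhere else to go.

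*Bias is not shown.* A reader might infer that women who stop early are restless, contracting or unwell, that agreement is worse in them, and that the limits are therefore flattered. That is plausible, but no passage says it. Section 9.5.1 also drops points with invalid signals, so many of the worst minutes would stay out after any change. With one 30-minute paired session, few women may be affected.

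*The exclusions will be visible.* Section 9.6.3 lists them. That helps, but a list does not show what the limits would have been.

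**Conclusion.** The point holds as an unreconciled conflict between 9.5.1 and 5.2.1 in the definition of the only performance set, together with a circular definition of completion in 7.5. It should be corrected before analysis.

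Its numerical effect is unknown. It is small if the SD is near 1.15 bpm, or if women who stop early agree as well as finishers. In the assumed scenarios the upper FHR limit passes 7 bpm in one of eight, which needs the doubled finisher SD, 20% stopping and an SD of 8 bpm in those women. The documents therefore do not support a claim that the rule would turn failure into success, or that the planned result is biased in a known direction. The loss of power is modest: 90.0% to 86.5% if 5 of 50 women are lost at SD 2.28. It could be offset by recruitment, since 50 is a minimum and the synopsis allows up to 200.

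The case for change rests on the text and on the estimand, and does not depend on the scenarios.

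**What to change.** - In 9.5.1, drop finishing as a condition. Include every enrolled woman without a major protocol violation who has at least one valid paired minute, whatever her completion status, and use all her valid paired minutes up to disconnection or withdrawal.
- Keep the major-violation condition. Define major in advance and state that stopping early is not in itself a major violation.
- Align 7.5 with 9.5.1 on whether any violation or only a major one counts, and give completion a definition that does not rely on the word finished.
- Report the finishers-only result as a sensitivity analysis for FHR, MHR and contractions.

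The cost is a few sentences and one extra analysis run. Sample size and study procedures do not change. The downside is that the limits of agreement may come out slightly wider.

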9.5.2 Statistical Analysis of Analysis Sets

The SA set will serve as the analysis set safety assessments. The performance assessments will be performed on the PA set.

9.6 Statistical Analysis

9.6.1 General Considerations

Statistical analyses will be performed using SAS® v9.4 or higher (SAS Institute, Cary NC, USA). Statistical analyses and reporting will be performed in compliance with FDA Guidance E6 GCP and E9 and ISO 14155.

Baseline demographic together with safety analyses will be performed on all subjects if the SA set. Baseline values are defined as the last valid value prior to study device use.

If statistical tests are performed, nominal p-values will be presented. All statistical tests will be two-sided. Where confidence limits are appropriate, a two-sided 95% confidence interval will be constructed.

For comparison of means (continuous variables), the two-sample t-test or the Wilcoxon rank sum test will be used as appropriate. For comparison of proportions (categorical variables), the Chi-squared test or Fisher's exact test will be used as appropriate.

If multiple measurements are taken in a single subject, statistics will be appropriately modified to accommodate the within subject correlation.

9.6.2 Demographic and other baseline variables

Demographic and baseline pregnancy related characteristics will be tabulated. Continuous variables such as age and BMI will be summarized by a mean, standard deviation, minimum, median and maximum, and categorical variables by a count and percentage.

9.6.3 Disposition of subjects

Subject disposition will be tabulated; the number of enrolled, exposed to study device, prematurely terminated and completed as planned subjects will be summarized, including the number of subjects in each analysis population. Device tolerability and compliance will be presented, the number and percent of subjects who fail to complete the study and the number and percent of subjects who fail to complete the study because of adverse events will be presented. A list of discontinued subjects, protocol deviations, and subjects excluded from the performance analyses will also be provided.

9.6.4 Performance analysis

9.6.4.1 Primary performance:

Fetal heart rate (FHR) and maternal heart rate (MHR) will both be analyzed in a similar manner as follows:

A comparison between PregSense™ measurement of FHR and MHR versus the reference measurements (i.e. CTG) are made using methods described by Bland and Altman¹².

The correlation (Pearson's correlation coefficient) and mean difference between the reference and PregSense™ measures of FHR and MHR will be presented together with a 95% confidence interval. A high correlation and a mean difference value near zero are expected if the two devices (Reference vs. PregSense™) output the same values.

In addition, a Bland-Altman plot of the mean versus the difference will be presented, and the 95% limits of agreement calculated together with respective confidence intervals. As a measure of accuracy, the mean bias and its standard deviation (with 95% confidence intervals) are estimated from random effects analysis of variance models programmed in SAS® using the MIXED procedure. This is done to accommodate the within subject correlation due to repeated FHR and MHR measurements.

Linear regression models (Deming or Passing-Bablok regression as appropriate) will be fitted to the values obtained from both devices of FHR and MHR; the slope and intercept together with respective 95% CI 's will be presented. The confidence intervals of the regression parameters will be calculated with bootstrap methodology using 10,000 simulated samples as well.

9.6.4.2 Secondary performance:

Uterine contractions as measured by PregSense™ and the standard of care (i.e. CTG including TOCO recordings), are measured continuously for a duration of 30 minutes with data sampling taken at 1-minute intervals in parallel with both study devices. We shall count the number of contractions (may be more than one per subject) as determined by the blinded assessors at each time point for which there was agreement between the PregSense™ and the standard of care. The percent of agreement (i.e. positive agreement) will be presented, the denominator of this fraction will be the standard of care number of identified contractions per subject. The binary positive agreement variable will be modeled with a

¹² https://en.wikipedia.org/wiki/Bland%E2%80%93Altman_plot

**CLINICAL STUDY EVALUATING THE SAFETY OF THE NON-INVASIVE
PRESENSE™ AND COMPARATIVE PERFORMANCE OF PRESENSE™
VERSUS CTG INPRENATAL MONITORING OF PREGNANT SUBJECTS**

Ref. No.: CLP1000

Rev. 05

Page 33 of 42

repeated measures model for binary data using the GENMOD procedure in SAS (link=identity dist=bin). This is done to accommodate the within subject correlation due to repeated measurements. The intercept of the model is the parameter of interest; this will be presented with corresponding 95% confidence interval. A point estimate for the agreement that is considered acceptable is 85%. Note that if the agreement will be 100% a Wilson score confidence interval will be presented instead.

The false positive alert rate will be analyzed in a similar manner. At each time point, no notation of a contraction by each of the modalities will be considered negative for uterine contraction, therefore the false positive alert rate will count the number of falsely identified contractions by the PregSense™ relative to the SOC.

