9.4 Sample Size Justification

The company intends to recruit a minimum of 50 subjects for this study. An attempt will be made to include 5 subjects with contractions per site.

The minimum recommended number of measurements for a method comparison study as per EP09-A3: "Measurement Procedure Comparison Bias Estimation Using Patient Samples Approved Guideline – Third Edition") is a sample size of 40 laboratory samples (subjects in our case). The devices will record for 30 minutes with data sampling at 1-minute intervals, i.e. each subject may have up to 30 minutes measurements of FHR and MHR available for analysis, but no less than 1 minute of paired corresponding detection data with both modalities. We expect that on average there will be at least 5 paired measurements per subject. Therefore, if at least 50 subjects are recruited for the study there will be up to 1000 measurements of heart rate with both devices and no less than 250.

¹¹ http://beijingyes.com/download/Holter_2_Accuracy_and_reliability_of_fetal_heart_rate_monitoring.pdf

In addition, from preliminary company data the mean difference between FHR measurements with two methods was 0.695BPM (SD= 1.15BPM), using the sample size equation from Lu MJ, Zhong WH, Liu YX, Miao HZ, Li YC, Ji MH (2016) Sample size for assessing agreement between two methods of measurement by Bland-Altman method. The International Journal of Biostatistics 12: issue 2 (pp. 8), we find that with a sample size of at least 50 subjects the acceptance criterion can be met at a 5% level of significance and with 90% power even if the standard deviation is almost twice as high as seen in the feasibility study.

An acceptable outcome for the secondary performance measure of Uterine contractions agreement is 85%, in order to estimate this parameter with a two-sided 95% exact binomial confidence interval having a half-width of $\pm 10\%$ at least 65 contractions are required. If each subject experience at least 2 contractions and the within subject correlation is moderate ($r=0.5$) then a sample size of 44 women will be sufficient to measure this endpoint with acceptable reliability.

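### The contraction-agreement interval, if computed in the usual identity-link way, covers about 85 to 91% instead of 95% for true agreement from 85% to about 96.5% in the planned design, errs in the device's favour, and can exceed 100%

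*Combined protocol and SAP*

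**What the plan says.** Section 9.6.4.2 of the combined protocol and SAP models positive agreement between PregSense and the standard of care with a "repeated measures model for binary data using the GENMOD procedure in SAS (link=identity dist=bin"). It continues: "The intercept of the model is the parameter of interest; this will be presented with corresponding 95% confidence interval". Neither the type of interval, the standard error nor the working correlation is named. Section 9.6.1 adds only that "Where confidence limits are appropriate, a two-sided 95% confidence interval will be constructed".

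One exception is made: "Note that if the agreement will be 100% a Wilson score confidence interval will be presented instead". Acceptability in the same section is set on the estimate alone: "A point estimate for the agreement that is considered acceptable is 85" per cent.

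Section 9.4 sizes the endpoint for a "two-sided 95% exact binomial confidence interval having a half-width of" ±10% and says that "at least 65 contractions are required". It then arrives at 44 women, assuming at least 2 contractions each and a within-subject correlation of 0.5. The false-positive rate is to be analysed in a similar way.

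**The concern.** On the identity scale the intercept is the proportion itself, and an interval of estimate ± 1.96 standard errors is symmetric and has no ceiling. Agreement of 85% or more from a few dozen women has a skewed sampling distribution: the estimated standard error shrinks as the estimate approaches 100%. High estimates therefore come with intervals that are too short, and the lower limit sits too high.

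The plan recognises the boundary at exactly 100% observed agreement but keeps the symmetric interval just below it. Because acceptability is a point estimate, this interval is the reported measure of how firmly the data support the figure. If it is too short, and short on the side that flatters the device, a reader will think agreement better established than it is. An upper limit above 100% is also impossible for a proportion.

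**Working it through.** **The plan's own figures.** At 85% agreement, the average exact half-width is 10.0% at 57 contractions, 9.9% at 58 and 9.3% at 65, so 65 is more than the stated target needs. With 2 contractions per woman and r = 0.5 the design effect is 1 + (2 − 1) × 0.5 = 1.5. Then 65 × 1.5 / 2 = 48.75, or 49 women, whereas 58 × 1.5 / 2 = 43.5, or 44 women. The 44 thus matches 58 contractions rather than 65. That is a separate matter. The plan's 44 is used below, and 49 women does not change the conclusion (coverage 92.4% at true 85%, 91.9% at 90%, 84.2% at 95%).

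**Inputs.** From section 9.4: K = 44 women, 2 contractions each, r = 0.5. From section 9.6.4.2: identity link, and Wilson at 100%. Assumed: estimate ± 1.96 cluster-robust standard errors, and Wilson computed on all 88 contractions.

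**Method.** Exact enumeration. For true agreement p, a woman has 2, 1 or 0 agreements with probabilities
- p₂ = p² + r·p(1 − p)
- p₁ = 2p(1 − p)(1 − r)
- p₀ = (1 − p)² + r·p(1 − p)

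At p = 0.85 these are 0.78625, 0.1275 and 0.08625. For a, b and c women with 2, 1 and 0 agreements:
- p̂ = (2a + b) / 2K
- SE = √[a(2 − 2p̂)² + b(1 − 2p̂)² + c(2p̂)²] / 2K
- interval p̂ ± 1.96·SE; if a = K, Wilson with lower limit 1 / (1 + 1.96²/88) = 95.8%

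Multinomial probabilities are summed over all outcomes.

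| True agreement | Coverage | Lower limit above truth (nominal 2.5%) | Upper limit above 100% | Coverage, logit-scale t interval |
|---|---|---|---|---|
| 85% | 91.4% | 7.3% | 0.9% | 96% |
| 90% | 89.9% | 9.4% | 10% | 96% |
| 95% | 88.4% | 11.2% | 56% | 94% |
| 96.5% | 84.7% | 15.0% | 71% | 97% |
| 97% | 99.8% | 0.0% | 73% | 97% |
| 99% | 100.0% | 0.0% | 48% | 96% |

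**Why undercoverage stops near 96.5%.** The highest lower limit the symmetric interval can give comes from 87 of 88: p̂ = 0.9886, SE = 0.01123, lower limit 0.9886 − 1.96 × 0.01123 = 96.7%. At 88 of 88 the Wilson lower limit is 95.8%. No outcome can put the lower limit above a truth higher than 96.7%. The perfect result also gets a lower limit below that of the result with one disagreement.

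The same sum gives 94.2% for 25 women (49 of 50, SE 0.01960) and 98.5% for 100 women (199 of 200, SE 0.00497). The end of the affected range therefore moves with size.

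**Other settings (2 contractions each, r = 0.5).**
- 25 women: coverage 90.1% at 85% and 85.4% at 90%, but 99.7% at 95%.
- 100 women: 93.5% at 85% and 92.8% at 90%.
- 44 women with unequal counts averaging 2 (simulation): 91.2% at 85%, 85.4% at 95%, 98.8% at 97%.

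**A single example.** With 95% observed, effective size 88 / 1.5 = 58.7 and SE = √(0.95 × 0.05 / 58.7) = 0.0285, the interval is 89.4% to 100.6%. The logit-scale t interval with the correction K/(K − 1) on the variance gives 84.8% to 98.5%.

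**The case against.** **The interval type is inferred.** This stands. The plan says only that a corresponding 95% interval will be given. The reading taken is the ordinary one for an identity-link intercept, but the figures depend on it.

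**A reader might infer that the interval fails all the way to 99%.** The documents do not support that. The plan prespecifies one combined procedure, and its Wilson rule lifts coverage above 99% from about 97% upward with 44 women. Without that rule, coverage at 97, 98 and 99% would be 86.4, 73.5 and 48.4%.

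**A reader might infer that the lower limit protects the 85% claim.** It does not. Section 9.6.4.2 sets acceptability on the point estimate, and section 9.3 ties study success to the heart-rate limits of agreement. Changing the interval changes no decision.

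**A reader might call it an error to size on an exact interval and analyse with a clustered model.** Section 9.4 allows for within-subject correlation, so this difference is not in itself a fault.

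**25 women is not the plan's size.** This stands. It multiplies a target of 5 women per site by 5 sites, while the synopsis allows more sites and up to 200 subjects. With 100 women the shortfall at 85 to 90% is mild.

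**The false-positive rate.** A mirror-image fault near 0% is plausible, but its size was not computed. That analysis runs over time points without a contraction, so there are more observations per woman and the figures above do not carry over.

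**Conclusion.** The point holds as a misstatement of precision on a secondary endpoint. In the planned design, a nominal 95% interval covers roughly 85 to 91% at the tabulated true values from 85% to 96.5%. Almost all of the error is a lower limit that is too high, and an upper limit above 100% is more likely than not at true 95%. Above about 97% the interval is conservative instead. The upper end of the affected range is about 94% with 25 women and about 98.5% with 100.

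This rests on a z-based interval with a robust standard error, 2 contractions per woman, r = 0.5, and Wilson applied to all contractions. It does not bear on whether the device is judged acceptable or the study successful.

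**What to change.** In section 9.6.4.2, name the interval. Fit the same GENMOD model with a logit link, use t quantiles with (women − 1) degrees of freedom and a small-sample-corrected robust standard error, and back-transform the estimate and limits. Keep the Wilson rule at 100%. Data and estimand are unchanged, and no limit can pass 100%. Use the same bounded interval for the false-positive rate, for consistency.

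At the values in the table this covers 94 to 97% with 44 women. A finer grid shows one dip, to 91.3% near 95.75%. It arises because the Wilson interval is taken on 88 contractions as if they were independent. The SAP should state which sample size that rule uses; with the effective size of 58.7 the dip disappears.

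The cost is one SAP paragraph and a modest program change: link, quantile, standard-error correction and back-transformation. The downside is a less favourable lower limit: by the same formulas about 3 points at 85% observed (75.9% to 72.9%) and about 4.6 points at 95% observed (89.4% to 84.8%).

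### At 100% contraction agreement the Wilson fallback in 9.6.4.2 carries no adjustment for clustering, so its lower bound would be about 2 to 3 points too high at 25 to 44 women with two contractions each

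*Combined protocol and SAP*

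**What the plan says.** Section 9.6.4.2 counts contractions, possibly several per woman, and takes the contractions identified by the standard of care as the denominator of positive agreement. The binary agreement variable goes into a "repeated measures model for binary data using the GENMOD procedure in SAS (link=identity dist=bin"). The stated reason is: "This is done to accommodate the within subject correlation due to repeated measurements". The intercept is reported with a 95% confidence interval.

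At complete agreement a different rule applies: "Note that if the agreement will be 100% a Wilson score confidence interval will be presented instead". The sentence does not say whether the interval is computed on contractions, women or an effective sample size. The false positive alert rate is to be analysed in a similar manner.

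Three other statements bear on the point:

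- Section 9.4 plans this endpoint with clustering: "If each subject experience at least 2 contractions and the within subject correlation is moderate" (r = 0.5), 44 women are said to be enough.
- Section 9.6.1 has a general rule: "If multiple measurements are taken in a single subject, statistics will be appropriately modified to accommodate the within subject correlation".
- On acceptance, section 9.6.4.2 says: "A point estimate for the agreement that is considered acceptable is 85"%.

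**The concern.** A Wilson score interval assumes independent trials. If two contractions in the same woman tend to be classified alike, the second adds less information than the first. An interval that counts both in full is then too narrow.

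The plan accepts this for the main analysis and for the sample size. At 100% agreement it names an interval that carries no such allowance. What is at stake is the reported lower confidence bound when agreement looks perfect, which is the figure a reader would use to judge how far below 100% the true agreement could be.

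**Working it through.** **Inputs.**
- Two-sided 95% level (9.6.1), so z = 1.96 and z² = 3.84.
- At least 2 contractions per woman, r = 0.5, 65 contractions and 44 women (9.4).
- An attempt to include 5 women with contractions per site (9.4) and up to 5 centers (synopsis), so about 25 women. This is a target, not a guarantee.

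**The plan's own figures first.** At 85% agreement the exact binomial interval has a half-width of 9.3% with 65 contractions. The half-width first falls to 10% or less at 58 contractions (9.9%). With m = 2 and r = 0.5 the design effect is 1 + (2 − 1) × 0.5 = 1.5.
- 65 contractions need 65 × 1.5 / 2 = 48.75, so 49 women.
- 58 contractions need 58 × 1.5 / 2 = 43.5, so 44 women.

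The stated 65 and 44 therefore do not fit together under the standard design effect. That is a separate matter and does not alter the direction of what follows. I use the stated 44 women.

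**Wilson lower bound at 100% agreement.** With all n units agreeing, the bound reduces to n / (n + z²). The unadjusted version takes n as the number of contractions. The adjusted version takes n divided by the design effect.

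| Women × contractions | Unadjusted | Effective n | Adjusted, r = 0.5 |
|---|---|---|---|
| 44 × 2 | 88 / 91.84 = 95.8% | 88 / 1.5 = 58.67 | 58.67 / 62.51 = 93.9% |
| 25 × 2 | 50 / 53.84 = 92.9% | 50 / 1.5 = 33.33 | 33.33 / 37.17 = 89.7% |

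The gap is 1.9 points in the first case and 3.2 in the second (before rounding).

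**Sensitivity to r, 44 × 2.** With r = 0.35 the adjusted bound is 94.4%. With r = 1, which amounts to counting women, it is 44 / 47.84 = 92.0%.

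**Check of the error rate.** For two contractions with agreement probability p and correlation r, the chance that both agree is p² + r p(1 − p). Set p at the unadjusted bound for 44 × 2, p = 0.9582:
- Independence: 0.9582^88 = 2.3%, close to the nominal 2.5%.
- r = 0.5: (0.9182 + 0.5 × 0.9582 × 0.0418)^44 = 0.9382^44 = 6.0%.

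So under the plan's own correlation, true agreement at the stated lower bound would produce 100% observed agreement about 6% of the time, more than twice the nominal lower-tail error. The corresponding figure for 25 × 2 is 6.3%.

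**Check of the adjustment.** Setting [p² + 0.5 p(1 − p)]^44 equal to 0.025 and solving for p gives an exact lower bound of 94.5%, against 95.9% by the same method at r = 0. The effective-n Wilson bound of 93.9% is slightly cautious, and the direction is confirmed.

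**Where the adjusted bound would fall below 85%.** The condition n / (n + 3.84) < 0.85 requires an effective n below 0.85 × 3.84 / 0.15 = 21.8. As an assumed case, 15 women × 2 gives 30 / 33.84 = 88.6% unadjusted and 20 / 23.84 = 83.9% adjusted.

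**The case against.** **The text does not say the interval is unadjusted.** Section 9.6.4.2 names a method but no unit, and the general rule in 9.6.1 could be read as requiring a modification here too. This stands in part: it is an inference that every contraction would be counted as independent. But 9.6.1 does not say how to modify the interval, and the specific rule replaces the clustered analysis with a named binomial one. The data cannot fill the gap either, because r cannot be estimated when every contraction agrees. It has to be fixed beforehand.

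**A fallback is unavoidable.** This stands. With no residual variation the model has no usable standard error; a trial repeated-measures fit to 88 agreeing contractions returned no value. Moving away from the model is not the fault. The missing allowance for clustering is.

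**A reader might infer that the fallback could wrongly place the lower bound above 85% and so change the outcome.** The documents do not support that. The 85% figure is a point-estimate criterion for a secondary endpoint, and the success criterion in 9.3 concerns fetal and maternal heart rate only. At 44 or 25 women with 2 contractions each, the adjusted bound stays above 85%. Crossing needs few contributing women. For example, 65 contractions at an assumed 6 per woman give a design effect of 1 + 5 × 0.5 = 3.5 and an adjusted bound of 18.57 / 22.41 = 82.9%, but that is only about 11 women, and neither 6 per woman nor 11 women is in the plan. With 6 per woman in 25 women, the adjusted bound is 42.86 / 46.70 = 91.8%.

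**Conclusion.** The point holds as a minor defect in a reported interval. Followed as written, and computed on contractions, the fallback gives a lower bound about 2 points too high at the planned 44 women × 2 and about 3 points too high at 25 × 2. This rests on the plan's own r = 0.5 and 2 contractions per woman, and on contractions being the unit, which is the natural reading given the denominator in 9.6.4.2. The gap would be larger only if few women contribute, which is an assumption. No success decision depends on it.

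The same boundary problem arises if the false positive rate is 0%, since that rate is handled in a similar manner and no boundary rule is given for it.

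**What to change.** Add to section 9.6.4.2: at 100% agreement, the Wilson interval is computed with effective n = contractions / [1 + (m − 1)r], where m is the mean number of contractions per woman and r is fixed in advance at the section 9.4 value of 0.5. State that the same rule applies if the false positive rate is 0%, with m the mean number of denominator units per woman for that rate. The section should name that denominator, because it determines m.

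The cost is one or two sentences and a slightly lower reported bound at 100% agreement. For the false positive rate the cost is a higher upper bound, and the increase grows with m. No change to data collection or sample size is needed.
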